1.7. Risk-Benefit Assessment

BGB-290 has been studied in nonclinical toxicity and Phase 1 clinical studies. BGB-290 toxicities are largely consistent with the safety profile shared by other PARP inhibitors.

MDS and AML have been reported in a small number (< 1%) of patients treated with PARP inhibitors, especially in patients harboring a germline BRCA mutation ([Ricks et al, 2015](#)). Typically, patients who develop MDS and AML while on therapy with a PARP inhibitor have a history of extensive previous chemotherapy and some have a history of previous cancer or bone marrow abnormalities. To date, there have been no reports of MDS or AML in patients treated with BGB-290. Patients in this study will be monitored monthly for hematological toxicities and events of MDS and AML will be reported as SAEs irrespective of time elapsed since end of study treatment.

Given that patients with advanced gastric cancer currently have no treatment options after completion of first-line therapy, the risk of BGB-290 toxicities appears acceptable considering the strong rationale for exploring PARP inhibition in the maintenance setting.

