5.6.2. Long-term Follow-up

Patients will be followed for survival, further anticancer therapy, and diagnosis of MDS or AML via telephone contact or other means (eg, clinic visit) approximately every 12 weeks until death, withdrawal of consent, or the end of study, whichever occurs first ([Appendix 1](#)).

Patients who were permanently discontinued from study drug for reasons other than PD and meet criteria otherwise (eg, discontinued for AE and no new anticancer therapy) will be followed with tumor assessments every 8 weeks (± 7 days) until PD or any other reason listed in [Section 5.7](#), whichever occurs first. For efficacy assessments as per protocol, refer to [Section 7.3.2](#) and [Appendix 1](#). If the patient refuses to return for these tumor assessments or is unable to do so, every effort should be made to contact the patient by telephone to determine the patient's disease status and survival.

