9.3. Timing, Frequency, and Method of Capturing Adverse Events and Serious Adverse Events

9.3.1. Adverse Event Reporting Period

After the ICF has been signed, but before initiation of study drug, only SAEs should be reported.

After initiation of study drug, all AEs and SAEs, regardless of relationship to study drug, will be reported until 30 days after the last dose of study drug or initiation of new anticancer therapy, whichever occurs first. After this period, the investigator should report any SAEs that are believed to be related to prior study drug.

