9.4.6. Myelodysplastic Syndrome and Acute Myeloid Leukemia

Events of MDS or AML should be treated as medically serious, even if the patient is not admitted to a hospital. These events should be reported to the sponsor irrespective of the time elapsed since the end of study treatment (see Section 9.7).

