10.6.2. Adverse Events

The AE will be coded using MedDRA Version 22.0 or higher and graded using the current version of NCI-CTCAE.

A TEAE is defined as an AE that had an onset date on or after first study treatment or was worsening in severity from baseline (pretreatment) up to 30 days following permanent study drug discontinuation or initiation of new anticancer therapy, whichever occurs first. All TEAEs will be included in summary tables and in-patient data listings.

The incidence of TEAEs will be reported as the number (percentage) of patients with TEAEs by system organ class (SOC) and preferred term (PT). A patient will be counted only once by the highest grade according to NCI-CTCAE Version 4.03 within an SOC and PT, even if the patient experienced more than one TEAE within a specific SOC and PT. The number (percentage) of patients with TEAEs will also be summarized by relationship to the study treatment.

Treatment-related AEs include those events considered by the investigator to be related to study treatment or with missing assessment of the causal relationship. Serious AEs, deaths, TEAE of Grade ≥ 3 , study drug-related TEAEs, and TEAEs that led to study drug withholding or permanent discontinuation will also be summarized.

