6.5.2 Adverse Events

AEs will be graded by the investigators using NCI CTCAE v4.03. The AE verbatim descriptions (investigator terms from the CRF) will be classified into standardized medical terminology using the Medical Dictionary for Regulatory Activities (MedDRA). Adverse events will be coded to the MedDRA (Version 22.0 or higher) lower level term closest to the verbatim term. The linked MedDRA preferred term (PT) and primary system organ class (SOC) are also captured in the database.

A treatment-emergent adverse event (TEAE) is defined as an AE that had an onset date on or after the date of the first dose of study treatment through 30 days after the last dose (permanent discontinuation of study treatment) or initiation of new anticancer therapy. Only those AEs that were treatment emergent will be included in summary tables. All AEs, treatment emergent or otherwise, will be presented in patient data listings.

An overview table of patients with at least one TEAE will be presented, as the number (percentage), with the incidence of following:

- patients with any TEAE
- patients with any TEAE with Grade 3 or higher
- patients with any serious TEAE
- patients with any TEAE leading to death
- patients with any TEAE leading to treatment discontinuation
- patients with any TEAE leading to dose modification
 - patients with any TEAE leading to dose interruption
 - patients with any TEAE leading to dose reduction
- patients with any treatment-related TEAE
- patients with any treatment-related TEAE with Grade 3 or higher
- patients with any treatment-related serious TEAE

- patients with any treatment-related TEAE leading to death
- patients with any treatment-related TEAE leading to treatment discontinuation
- patients with any treatment-related TEAE leading to dose modification
 - patients with any treatment-related TEAE leading to dose interruption
 - patients with any treatment-related TEAE leading to dose reduction

Summaries of all above TEAEs will also be reported as the number (percentage) of patients by SOC and PT.

Summaries of all TEAEs, SAE, Grade 3 or higher TEAEs, treatment-related TEAEs, and TEAE leading to treatment discontinuation will also be provided by PT only in descending order of frequency.

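### MDS/AML and drug-related SAEs with onset after the treatment-emergent window are collected under the protocol, but the SAP's restriction to TEAEs keeps them out of the by-arm adverse event counts

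*SAP*

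**What the plan says.** **What is tabulated.** SAP 6.5.2 treats an AE as treatment-emergent if its onset falls from the first dose "through 30 days after the last dose (permanent discontinuation of study treatment) or initiation of new anticancer therapy". It then restricts the tables: "Only those AEs that were treatment emergent will be included in summary tables". Other AEs go to patient listings. The overview rows are worded in TEAEs, including serious TEAEs and treatment-related serious TEAEs. SAP 6.5 has no table for MDS/AML, for events of special interest or for post-treatment SAEs. SAP 6.5.3 separately summarizes deaths and causes of death by arm, including those in survival follow-up.

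**What is collected.** Protocol 1.7 says that "events of MDS and AML will be reported as SAEs irrespective of time elapsed since end of study treatment". Protocol 9.4.6 repeats the rule: "These events should be reported to the sponsor irrespective of the time elapsed since the end of study treatment". Protocol 5.6.2 adds active follow-up: "Patients will be followed for survival, further anticancer therapy, and diagnosis of MDS or AML", about every 12 weeks until death, withdrawal of consent or end of study. For the time after the 30-day or new-therapy limit, Protocol 9.3.1 says: "After this period, the investigator should report any SAEs that are believed to be related to prior study drug". Protocol 9.7 carries both duties past the patient's discharge from the study.

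**The protocol's own window.** Protocol 10.6.2 runs the TEAE window "up to 30 days following permanent study drug discontinuation or initiation of new anticancer therapy, whichever occurs first". The SAP leaves out the final qualifier.

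**The concern.** The protocol names MDS and AML as recognized adverse events of PARP inhibitors (1.4.2.3) and relies on continued reporting of them in its risk-benefit assessment (1.7). The SAP gives that follow-up no place in any adverse event table. A patient who progresses, starts second-line therapy and is diagnosed with MDS eight months after the last dose adds nothing to the serious TEAE row. Neither does a drug-related SAE on day 40 after the last dose.

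What is at stake is the summary by arm of a rare, serious event. With so few cases expected, omitting one can turn a reported count of one into zero. This follows from a stated rule, not from missing detail.

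**Working it through.** **1. Where each event would appear, applying the SAP's restriction as written**

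| Event | Collected under the protocol | AE summary tables (SAP 6.5.2) | Listings (SAP 6.5.2) | Death summary (SAP 6.5.3) |
|---|---|---|---|---|
| MDS/AML, onset in window | yes | yes | yes | if fatal |
| MDS/AML, onset after window | yes (1.7, 5.6.2, 9.4.6, 9.7) | no | yes | if fatal |
| Related SAE, onset after window | yes (9.3.1, 9.7) | no | yes | if fatal |

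**2. The conflict over SAEs.** Three places in the SAP plan a summary of SAEs without the treatment-emergent label that neighbouring categories carry: the opening of 6.5, the by-preferred-term summary in 6.5.2, and the summary by SOC, preferred term and maximum severity in 6.5.2. There are two readings:

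- If these mean serious TEAEs, late events are excluded.
- If they mean all SAEs, they contradict the restriction. Late MDS/AML would then reach the SAE tables. Late related SAEs would still be missing from the treatment-related serious TEAE row, and there would be no single MDS/AML count with time to onset.

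Both readings need a text change.

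**3. Scale.** The plan gives no figure on this point to reproduce. The inputs are 64 patients per arm (Protocol 10.7, SAP 5; all assumed dosed) and a class frequency stated only as below 1% (Protocol 1.7). The rates p below are assumptions within that bound.

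Expected cases = 64 × p. Chance of at least one = 1 − (1 − p)^64.

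- p = 0.1%: 64 × 0.001 = 0.064 cases; 1 − 0.999^64 = 6%
- p = 0.5%: 64 × 0.005 = 0.32 cases; 1 − 0.995^64 = 27%
- p = 1%: 64 × 0.01 = 0.64 cases; 1 − 0.99^64 = 47%

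These cover cases at any time, including those that are tabulated.

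**4. The post-window part.** A simulation gave the share f of follow-up that falls outside the window by month 26. Taken from the plan were the 20-month accrual (assumed uniform) and a median PFS of 6.0 months, or 6.0/0.63 = 9.5 months. Assumed were exponential times, treatment until progression, median post-progression survival of 3, 6 or 9 months, and a window closing 0 or 30 days after progression. Across these settings f ran from about 15% to 44%.

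If the hazard is constant over follow-up (a further assumption), expected post-window cases = 64 × p × f, and the chance of at least one = 1 − (1 − pf)^64:

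- p = 0.1%: 0.064 × 0.15 = 0.01 to 0.064 × 0.44 = 0.03 cases; about 1% to 3%
- p = 0.5%: 0.32 × 0.15 = 0.05 to 0.32 × 0.44 = 0.14 cases; about 5% to 13%
- p = 1%: 0.64 × 0.15 = 0.10 to 0.64 × 0.44 = 0.28 cases; about 9% to 25%

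The documents give no rate for late related SAEs, so that part cannot be sized.

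**The case against.** The best case for the SAP has several parts, and much of it stands.

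- **The window is the protocol's.** Protocol 10.6.2 uses the same 30-day or new-therapy limit, and the safety objective (Protocol 2.2, SAP 3.2) is worded in TEAEs. The SAP tabulates what the objective names, and no protocol section promises a table of MDS/AML or of late related SAEs.
- **Nothing is lost.** Late events are listed, with separate listings for SAEs and treatment-related AEs. Fatal ones enter the by-arm death summary. With zero or one case expected, a listing shows much of what a table would.
- **The documents give no latency.** Protocol 1.7 sets reporting without a time limit but does not say that cases typically arise late. It speaks of patients who develop MDS or AML while on a PARP inhibitor, usually after extensive earlier chemotherapy, whereas patients here enter after first-line treatment.

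Three things remain. A listing is not a by-arm incidence, and the death summary catches only fatal cases. The exclusion itself is the SAP's: Protocol 10.6.2 says that TEAEs will be tabulated and that serious AEs will also be summarized, without ruling out other events, and SAP section 8 records no change to AE reporting. The unqualified SAE wording also leaves programmers to choose between two outputs.

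**Conclusion.** The point holds for events with onset after the window. Under the SAP's restriction, MDS/AML and related SAEs of that kind appear only in listings, or in the death summary if fatal. Because the unqualified SAE summaries conflict with that restriction, their absence from every table is likely but not certain until the text is reconciled.

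A reader might infer more than this, and the documents do not support it:

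- That the tables would show no MDS/AML at all. In-window cases are tabulated.
- That the safety objective is breached or a valid comparison of arms is lost. The objective concerns TEAEs, and counts this small support no formal comparison in either format.
- That 27% to 47% is the chance of an omitted case. It is the chance of any case at any time, at assumed rates in the upper half of the below-1% range. On the assumptions above, the chance of at least one post-window case in a 64-patient arm is about 1% to 25%.

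The consequence is modest and confined to safety reporting. The primary analysis is untouched. The change is still worth making, because the data are already being collected and the correction is small.

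**What to change.** Leave the TEAE tables as they are and amend SAP 6.5.2 as follows.

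1. Add a by-arm table of all MDS/AML diagnoses from first dose to last follow-up, regardless of the window or later therapy, with time from first dose and a footnote on subsequent anticancer therapy.
2. Add a separate by-arm table of SAEs judged related to study drug with onset after the window.
3. Amend the restriction so that it allows these two tables. For example: AE summary tables present TEAEs only, except the table of MDS/AML at any time and the table of post-window related SAEs.
4. State whether the SAE summaries in 6.5 and 6.5.2 cover serious TEAEs or all SAEs.
5. Restore 'whichever occurs first' to the TEAE definition, to match Protocol 10.6.2.

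Late SAEs should not be added to the existing serious or treatment-related TEAE rows. That would mislabel them and mix ascertainment periods, since after the window, apart from MDS/AML, only SAEs believed to be related are reported.

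The cost is SAP wording and two short tables. No new data collection is needed, and the sample size and efficacy analyses do not change. The downside is that late cases may be confounded by subsequent chemotherapy and the counts will be too small for a formal comparison. The tables should therefore be presented as descriptive.

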To confirm PK properties of BGB-290, blood samples will be taken at various time points as outlined in Section 7.6 and Appendix 1. Additionally, tumor tissue and blood samples will be obtained (as outlined in Section 7.7 and Appendix 1) to explore biomarkers of pharmacodynamics, response, and resistance to BGB-290 in gastric cancer.

Disease status will be assessed by the investigator using RECIST Version 1.1 (Appendix 2). Patients will undergo tumor assessments at screening and then every 8 weeks (± 7 days), or as clinically indicated.

There is no fixed duration of treatment.

[figure not shown]
Administration of BGB-290 or placebo will continue until PD, unacceptable toxicity, death, or another discontinuation criterion is met (Sections 5.5 and 5.7). Once the treatment phase has been completed, an EOT visit should occur within 7 days of stopping BGB-290 or placebo with subsequent phases of safety and long-term follow-up.

Long-term follow-up will include tumor assessments every 8 weeks (± 7 days) for those patients without PD, survival status, new anticancer therapy, and diagnosis of MDS or AML. Long-term follow-up will continue until the patient dies or another criterion for discontinuation from study is met (Section 5.7).

Once the study is completed and the study results are available, this study will be unblinded. For patients who have received BGB-290, the sponsor will continue providing the drug either on this study or through other options, ie, a roll-over study. Subjects who are on the Placebo arm will discontinue the study treatment.

Study procedures and assessments are detailed in Section 7 and Appendix 1. The study schema is provided in Figure 4.

Figure 4: Study Schema

Abbreviations: AML, acute myeloid leukemia; BID, twice daily; CR, complete response; ECOG, Eastern Cooperative Oncology Group; LOH, loss of heterozygosity; HRD, homologous recombination deficiency; MDS, myelodysplastic syndrome; PD, progressive disease; PO, oral; PR, partial response; q8w, every 8 weeks; ROW, rest of world; vs, versus.

Note: Key assessments during treatment phase: tumor assessments and patient-reported outcomes every 8 weeks, adverse events, hematology, and chemistry every 4 weeks. BGB-290 and placebo are to be administered continuously.

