4.2 SECONDARY ENDPOINTS

Efficacy assessment:

- OS, defined as the time from randomization to death due to any cause
- Time to second subsequent treatment (TSST), defined as the time from randomization until the second subsequent anticancer therapy or death after next-line therapy
- ORR, defined as the proportion of patients with a best overall response of CR or PR per RECIST Version 1.1 by investigator assessment
- DOR, defined as the time from the first documented confirmed response of CR or PR to PD per RECIST Version 1.1 by investigator assessment or death due to any cause, whichever occurs first
- Time to response, defined as the time from randomization to the first documented response of CR or PR per RECIST Version 1.1 by investigator assessment

Safety assessment:

- Incidence, timing, and severity of TEAEs, graded according to NCI-CTCAE Version 4.03 or higher
- Safety and tolerability assessment of laboratory measurements, vital signs, and ECG findings

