5 SAMPLE SIZE CONSIDERATIONS

This study is designed to provide 80% power for PFS. The following assumptions are used in determining the sample size for this study:

- Overall type I error rate: 0.1 (1-sided)
- Randomization: 1:1
- Median PFS for placebo group: 6.0 months
- PFS hazard ratio (HR; pamiparib/placebo): 0.63

A sample size of approximately 128 patients (64 per treatment group) is required to achieve 85 PFS events within the planned study duration of approximately 26 months after the first patient is randomized to study, assuming an estimated accrual period of 20 months.

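### TEAEs are reported only as crude percentages although observation time depends on PFS, and the timing part of the safety endpoint has no summary by arm

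*SAP*

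**What the plan says.** The safety objective (Protocol 2.2, SAP 3.2) compares the drug with placebo. SAP 4.2 gives the endpoint as "Incidence, timing, and severity of TEAEs, graded according to NCI-CTCAE Version 4.03 or higher".

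Protocol 3.1 sets no fixed treatment duration: "Administration of BGB-290 or placebo will continue until PD, unacceptable toxicity, death, or another discontinuation criterion is met". SAP 6.5.2 counts an event as treatment-emergent from the first dose through 30 days after the last dose or the start of new anticancer therapy.

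Every TEAE table in SAP 6.5.2 is a count and percentage of patients: the overview, the tables by preferred term in order of frequency, the tables by maximum severity, and the system organ class tables ("Summaries of all above TEAEs will also be reported as the number (percentage) of patients by SOC and PT"). Protocol 10.6.2 uses the same measure. SAP 6.5.1 summarises treatment duration, but no adverse event table uses it as a denominator. Neither document specifies an onset-time summary, a fixed-window table or a rate per unit of exposure. SAP section 8, which lists departures from the protocol, does not drop timing.

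**The concern.** There are two linked gaps.

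First, the endpoint has three components. Incidence and severity are each given tables; timing is not. This needs no modelling to establish.

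Second, follow-up for adverse events ends shortly after treatment ends, and treatment ends mainly at progression. If the drug prolongs PFS as the design assumes, pamiparib patients are observed longer. A crude percentage then mixes any drug effect on the event with the longer observation. The reader of the side-by-side tables could take an exposure difference for a toxicity difference, and the planned tables offer no way to separate the two.

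**Working it through.** **Inputs.** SAP section 5 gives "This study is designed to provide 80% power for PFS", "Randomization: 1:1", "Median PFS for placebo group: 6.0 months" and "PFS hazard ratio (HR; pamiparib/placebo): 0.63", with 1-sided type I error 0.1, 128 patients, 85 events, 20 months of accrual and 26 months in total. The documents give no adverse event rates for this trial, so those are assumed and shown as a range.

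**The plan's own figure.** Events = 4 × (1.2816 + 0.8416)² / (ln 0.63)² = 84.5, so 85. This reproduces the SAP. With exponential PFS and no dropout, 128 patients give 93.7 expected events by month 26. With an assumed 2% dropout per month they give 83.3. The stated calendar is therefore a fair basis for what follows.

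**Model.**
- Progression hazard per month: placebo ln 2 / 6 = 0.1155; pamiparib 0.63 × 0.1155 = 0.0728. Implied medians are 6.0 and 6.0 / 0.63 = 9.52 months.
- Follow-up to cutoff, C: uniform from 26 − 20 = 6 to 26 months.
- TEAE window: W = min(T + 30/30.4375, C), where T is time to progression.
- Crude incidence at a constant event hazard λ: the mean of 1 − exp(−λW).

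**Results with the same λ in both arms, cutoff at month 26.**

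| Quantity | Placebo | Pamiparib |
|---|---|---|
| Mean TEAE window (months) | 7.75 | 9.70 |
| Crude %, λ = 0.05 | 29.9 | 35.8 |
| Crude %, λ = 0.10 | 48.1 | 55.7 |
| First events per 100 patient-months, λ = 0.05 | 5.0 | 5.0 |
| First events per 100 patient-months, λ = 0.10 | 10.0 | 10.0 |

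With λ set to give a chosen placebo incidence, the percentages (placebo to pamiparib) are 10 to 12.3, 20 to 24.3, 30 to 35.9, 50 to 57.6 and 70 to 76.9. The excess is about 2 to 8 points.

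With full follow-up and no cutoff, incidence is 1 − exp(−λτ) × μ / (μ + λ), where μ is the progression hazard and τ = 30/30.4375. A placebo figure of 30% then becomes 39.6%. Over the same 10% to 70% range the excess is about 4 to 11 points.

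**When the excess is absent or reversed.**
- Event hazard confined to the first 1 to 2 months: 30% becomes 30.0% to 30.3%, and 50% becomes 50.0% to 50.4%.
- Extra pamiparib stopping hazard of 0.1155 − 0.0728 = 0.043 per month (about 23% over 6 months): the excess cancels, at 29.9% in both arms for λ = 0.05.
- Extra stopping hazard of 0.06 per month: the sign reverses, with 29.9% on placebo and 28.1% on pamiparib.

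**Limit of the person-time rate.** For an event confined to month 1 with 30% incidence in both arms, the mean person-time to first event is 5.57 and 6.93 months. The rates are 30 / 5.57 = 5.4 and 30 / 6.93 = 4.3 per 100 patient-months. That is a spurious deficit of about 20% in the longer-exposed arm.

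**The case against.** The strongest reply is that the bias is conditional and small. It needs a hazard that persists over treatment and treatment that ends mainly at progression. Protocol 5.5.1 lists other reasons to stop, including adverse events, withdrawal of consent and investigator's discretion. With 64 patients per arm, the standard error of a difference in proportions is √(2 × 0.3 × 0.7 / 64) = 8.1 points at 30% and 8.8 points at 50%, so the artefact is below one standard error. No test of adverse events is planned. SAP 6.5.1 shows treatment duration, so unequal exposure would be visible, and the SAP follows the measure that the protocol set.

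All of this stands as a limit on importance, and it means that the exposure point should be stated conditionally. It does not close the gap. A separate duration table tells the reader that exposure differs, but not how much of an observed difference in events it explains. The possibility of cancellation or reversal means that the direction cannot be read from crude tables alone.

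Two stronger readings are tempting and should be resisted. A reader might infer that the safety comparison is biased against pamiparib whenever PFS is positive. The calculations above show that it need not be. A reader might also infer that the trial cannot report timing. The documents do not support that: SAP 6.2.1 defines a safety study day, Appendix 10.1 imputes partial event dates, and adverse event listings are planned. What is missing is a specified summary, not data.

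**Conclusion.** The point holds in a limited form. The missing timing summary follows from the text alone. The exposure effect rests on exponential PFS at the design hazard ratio, treatment to progression, a constant and equal event hazard, and the month-26 cutoff. Under those assumptions crude incidence tends to be about 2 to 8 points higher on pamiparib for placebo incidences of 10% to 70%. The model ignores new anticancer therapy started within the 30 days, which would shorten the window. With equal PFS there would be no excess from this source. The consequence is for descriptive interpretation of a secondary objective; the primary analysis, sample size and error rate are untouched. This is a worthwhile improvement, not a flaw that threatens the trial.

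**What to change.** Keep the crude tables. Add to SAP 6.5.2, by treatment arm:

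1. Time to first onset, shown as cumulative incidence, for any TEAE, Grade 3 or higher, serious, and common preferred terms. This supplies the timing component and needs no constant hazard. State how death and the end of the TEAE window are handled: if the end of the window is counted as a competing event instead of censoring, the exposure difference comes back in.
2. As a supplement, exposure-adjusted incidence rates (patients with a first event per 100 patient-months at risk) for the same categories, with a note that they assume a roughly constant hazard and can understate early-onset events in the longer-exposed arm.

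The opening of SAP 6.5 refers to cohorts, which this two-arm trial does not have, so the new tables should name the arms explicitly.

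The cost is a few more tables from onset and dosing dates already collected, with no change to conduct.
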